5.3 Other Key Assessments (Data points)

The following time points will be collected on the electronic Case Report Forms (eCRFs): stroke symptom onset, admission to initial hospital/emergency department, if transferred, time of arrival to second hospital, diagnostic imaging, start of IV tPA, angio suite arrival, arterial puncture, time of each Trevo pass, clot integration, Trevo removal and end of procedure (defined as the time of the final cerebral angiogram).

Data on the use of accessory products during Trevo thrombectomy such as the balloon guide catheter (BGC) and intermediate catheters such as the distal access catheter (DAC) will be collected.

Trevo[®] Retriever Registry

De-identified images may be sent to a core lab for adjudication (e.g. CT/MRI scans and angiographies). Information will be collected on factors influencing health economics in the treatment of stroke such as costs of hospitalization, length of hospital stay and discharge disposition. The data collected will consist of hospital charges for cases involving real world use of the Trevo Retriever. . The UB-04 form will be collected within the United States while in other countries a CRF containing similar information will be completed. Collection of health economic information shall be disclosed to the subject in the Informed Consent Form (ICF).

6 Justification for the Registry Design

The data results from the TREVO and TREVO 2 trials demonstrate revascularization efficacy and safety of the Trevo Retriever. The Trevo Retriever Registry is a prospective, open-label, consecutive enrollment, multi-center, international trial. The purpose of the Trevo Registry is to assess the performance of the Trevo retriever in real world practice to increase knowledge on the performance of the device, monitor safety outcomes, detect rare complications, and to obtain information for potential improvements for next generation devices.

6.1 Method of Enrollment

Clinical data points will be evaluated in all subjects who meet the inclusion/exclusion criteria and where Trevo Retriever is used as the initial mechanical thrombectomy device to remove thrombus from the neurovasculature in the setting of acute ischemic stroke. For purposes of this registry, enrollment occurs when the Trevo Retriever is deployed through the compatible Microcatheter into the neurovasculature as the first mechanical neuro-thrombectomy device used to remove the thrombus.

A Screening and Enrollment Log will be maintained by each site to document basic information such as date screened and reason for screen failures for subjects who fail to meet the study eligibility criteria. In order to avoid bias, if a center chooses to participate in the Trevo Registry, every effort should be made to include all Trevo cases performed over a given duration of time in the registry. No site will be allowed to enroll more than 15% (300 subjects) of the entire maximum study population unless first approved by Stryker.

7 Study Population

7.1 Selection Criteria

7.1.1 Inclusion Criteria:

1. Subjects experiencing acute ischemic stroke who are eligible for restoration of blood flow using a Trevo Retriever in the neurovasculature to remove thrombus
2. Trevo Retriever is the initial mechanical neuro-thrombectomy device used to remove the thrombus
3. Signed Informed Consent obtained
4. Subject willing to comply with the protocol follow-up requirements
5. Anticipated life expectancy of at least 3 months

Trevo[®] Retriever Registry

7.1.2 Exclusion Criteria:

The subject is participating in another mechanical neuro-thrombectomy device trial or any other clinical trial where the study procedure or treatment might confound the study end point.

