STRYKER CONFIDENTIAL - THIS DOCUMENT CONTAINS CONFIDENTIAL AND PROPRIETARY INFORMATION THAT IS THE PROPERTY OF STRYKER CORPORATION. NEITHER THIS DOCUMENT NOR THE INFORMATION HEREIN MAY BE REPRODUCED, USED, OR DISCLOSED TO ANY THIRD PARTY WITHOUT THE PRIOR WRITTEN CONSENT OF STRYKER CORPORATION. CDM 10000023 Rev. AC

Trevo[®] Retriever Registry

Protocol Synopsis

Study Objective	
Primary Objective	To assess real world performance of the Trevo [®] Retriever which is intended to restore blood flow in the neurovasculature by removing thrombus in subjects experiencing ischemic stroke
Primary Endpoint	Revascularization status assessment at the end of the procedure using the modified TICI score
Secondary Endpoints	
 1. Day 90 mRS assessment 2. Day 90 all cause mortality 3. Neurological deterioration at 24 hours post procedure, defined as a four or more point increase in the NIHSS score from the baseline score 4. Rates of device and procedure related serious adverse events (AEs)
Other Key Assessments (Data points)	
 1. Time points will be collected on the following: stroke symptom onset, admission to initial hospital/emergency department, if transferred, time of arrival to second hospital, diagnostic imaging, start of Intravenous tissue Plasminogen Activator (IV tPA), angio suite arrival, arterial puncture, time of each Trevo pass, clot integration, Trevo removal and end of procedure (defined as the time of the final cerebral angiogram) 2. Data on the use of accessory products in conjunction with Trevo 3. Health economics, costs of hospitalization, length of stay, discharge disposition 4. Sub-study analysis of imaging (pre, angio, post) with an independent core lab measurement of ASPECTS, collaterals, modified TICI scores and core infarct volume. 5. Compare Day 90 outcome with pre-stroke mRS, baseline imaging and symptom onset to time of treatment.
Registry Device	Any approved Trevo Retriever approved for use by the local regulatory agency
Control	N/A
Device Sizes	All Trevo product sizes approved for use by the local regulatory agency
Study Design	
Study Design	Prospective, open-label, consecutive enrollment, multi-center, international registry
Planned Number of Subjects	Up to a maximum of 2000 subjects
Planned Number of Sites / Countries	Up to 100 sites worldwide
Efficacy Parameters	Post-procedural Modified TICI score

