4.1 Primary Objective

To assess real world performance of the FDA cleared/CE marked Trevo Retriever intended to restore blood flow in the neurovasculature by removing thrombus in patients experiencing ischemic stroke.

5 Registry Endpoints

Clinical data will be evaluated in all subjects where the Trevo Retriever is used as the initial thrombectomy device to remove thrombus from the neurovasculature in the setting of acute ischemic stroke.

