5.2 Secondary Data points

- a. Day 90 mRS (good clinical outcomes defined as mRS of 0-2)
- b. Day 90 mortality
- c. Neurological deterioration at 24 hours, defined as a four or more point increase in the NIHSS score from the baseline score
- d. Rates of device and procedure related serious AEs

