8.1 Written Informed Consent

A sample ICF is provided in **Appendix C** for the Investigator to prepare for use at the site. The written Informed Consent documents must be prepared in the language(s) of the potential subject population. The ICF must be approved by the study Institutional Review Board (IRB)/Ethics Committee (EC) and a copy provided to Stryker Neurovascular. Modifications to the form must be approved by Stryker Neurovascular prior to implementation. The document version must be identified on the ICF to maintain version control.

Written Informed Consent must be obtained for all subjects prior to data entry into the Trevo Retriever Registry electronic database. The subject or the subject's legally authorized representative (LAR) will be asked to sign the ICF. Consent should be obtained pre-procedure but depending on subject's acuity the consent may be obtained up to seven days post-procedure. No data may be entered into the database until written consent has been obtained. In the absence of informed consent, an IRB/EC approved waiver of consent and executed data use agreement must be in place.

Study personnel should document the consent process in the subject's medical record per Good Clinical Practice (GCP). The subject or LAR is to be provided a copy of the signed ICF.

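### Inclusion criterion 5 (3-month life expectancy) does not set aside the index stroke, so sites could leave out severe Trevo cases and lower the reported Day 90 mortality

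*Protocol*

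**What the plan says.** Criterion 5 in section 7.1.1, repeated in the synopsis, reads in full "Anticipated life expectancy of at least 3 months". Nothing in the protocol limits it to comorbid disease, tells sites to disregard the stroke being treated, or says what information may be used to judge it.

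The secondary endpoints include "Day 90 all cause mortality" (synopsis; section 5.2 has "Day 90 mortality") and the Day 90 mRS, with 0-2 counted as a good outcome and death scored 6 (Appendix F).

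The objective in section 4.1 begins "To assess real world performance of the FDA cleared/CE marked Trevo Retriever". Section 6.1 says, as a measure against bias, that "every effort should be made to include all Trevo cases performed over a given duration of time in the registry". The same section limits evaluation to eligible subjects: "Clinical data points will be evaluated in all subjects who meet the inclusion/exclusion criteria".

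On timing, section 8.2 lists confirmation of eligibility among the pre-procedure data, and Appendix D ticks it only in the pre-procedure column. Section 8.1 prefers consent before the procedure, but "depending on subject's acuity the consent may be obtained up to seven days post-procedure", and bars data entry until consent is in hand.

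**The concern.** The entry rule and two secondary endpoints look at the same period of about 90 days. In acute stroke the index event is a main driver of survival over that period: the protocol's own earlier studies report 90-day mortality of 20.0% and 33.0%. A rule on expected 3-month survival that does not set the stroke aside therefore selects on a strong predictor of the endpoint.

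There are two routes by which a treated case could be left out:

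- **Before the procedure.** A site reads the criterion literally and treats a patient with a severe stroke, but regards that patient as ineligible for the registry.
- **After the procedure.** Consent is sought late, the early course is already known, and that knowledge colours the judgement on criterion 5.

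Either route would make Day 90 mortality look lower and the mRS 0-2 rate look higher than in all Trevo cases. It would also work against the purpose in section 6 of monitoring safety and detecting rare complications. With up to 100 sites, different readings would add differences between sites that have nothing to do with the device.

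**Working it through.** **Reading the passages together**

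1. Criterion 5 has no exemption for the index stroke, in section 7.1.1 or in the synopsis.
2. Section 8.2 and Appendix D place the eligibility check before the procedure. Appendix D also ticks consent only in that column, yet section 8.1 allows consent up to Day 7. The column is therefore not a firm limit for every criterion. For a late-consent subject the full set of criteria cannot be confirmed before the procedure, because criterion 3 is the signed consent.
3. No sentence says that criterion 5 must be judged only on pre-procedure information when consent comes later.
4. The screening log in section 6.1 records basic items such as the reason for failure. No outcome is specified for those patients, so a loss could be counted but its effect on mortality could not be measured.
5. Appendix B restricts a protocol deviation to failure to obtain consent properly, so misapplying criterion 5 would not be recorded as one.

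**Inputs**

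- Earlier 90-day mortality: TREVO (Table 1) 12/60 = 20.0%; TREVO 2, Trevo arm (Table 4), 29/88 = 33.0%. Both reproduce.
- Maximum registry size: 2000 (synopsis).
- The protocol gives neither the share of Trevo cases left out (f) nor their 90-day mortality (d). Assumed here: f = 2% or 5%, d = 60% to 100%.

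**Formula.** With m the mortality in all Trevo cases, observed mortality = (m − f·d)/(1 − f). The downward shift is f·(d − m)/(1 − f).

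| m | f | d = 60% | d = 100% | Shift (points) |
|---|---|---|---|---|
| 20.0% | 2% | (0.200 − 0.012)/0.98 = 19.2% | (0.200 − 0.020)/0.98 = 18.4% | 0.8 to 1.6 |
| 20.0% | 5% | (0.200 − 0.030)/0.95 = 17.9% | (0.200 − 0.050)/0.95 = 15.8% | 2.1 to 4.2 |
| 33.0% | 2% | (0.3295 − 0.012)/0.98 = 32.4% | (0.3295 − 0.020)/0.98 = 31.6% | 0.6 to 1.4 |
| 33.0% | 5% | (0.3295 − 0.030)/0.95 = 31.5% | (0.3295 − 0.050)/0.95 = 29.4% | 1.4 to 3.5 |

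**Yardstick.** The 95% half-width at n = 2000 is 1.96·√(0.20·0.80/2000) = 1.8 points, or 1.96·√(0.3295·0.6705/2000) = 2.1 points. At f = 2% every shift lies inside the half-width. At f = 5% most exceed it.

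**Break-even.** The shift equals the half-width h when f = h/(d − m + h). For m = 20.0% this is 0.0175/0.8175 = 2.1% (d = 100%) to 0.0175/0.4175 = 4.2% (d = 60%). For m = 33.0% it is 0.0206/0.6911 = 3.0% to 0.0206/0.2911 = 7.1%.

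**mRS 0-2.** If none of those left out would have reached 0-2 (the extreme case), the rate rises by the factor 1/(1 − f). TREVO's 55.0% (33/60) becomes 0.550/0.98 = 56.1% or 0.550/0.95 = 57.9%. TREVO 2's 40.0% (34/85) becomes 0.400/0.98 = 40.8% or 0.400/0.95 = 42.1%.

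**Example from the protocol's own data.** In the TREVO 2 Trevo arm, 2 of 88 died within 24 hours, one death being device-related (Table 3). Without those two, mortality would read 27/86 = 31.4% instead of 33.0%, and the device-related death would disappear. This only illustrates what a few early deaths weigh; nothing says that these patients would have failed criterion 5.

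**The case against.** The case on the other side has real weight.

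- **Timing.** Eligibility belongs before the procedure, and the criterion is worded as a forecast. A reader might infer that a site completing the forms on Day 3, with the patient on comfort care, could properly record criterion 5 as not met. The documents do not support that: section 8.2 and Appendix D put the check earlier, and section 8.1 extends only the consent signature. It would be a misuse of the criterion. What stands on the concern's side is that nothing expressly bars such hindsight where consent is late.
- **Analysis population.** Section 6.1 sets enrollment at deployment of the device. Section 9.2 includes every consented subject with the device deployed and does not mention criterion 5. A consented, treated subject who deteriorates stays in. This protects only those who reach consent; a site that first decides criterion 5 is not met has no reason to seek it.
- **Early deaths are wanted.** Sections 8.4 to 8.6 collect cause and time of death and comfort-care status, and section 14 makes fatal events reportable through Day 90. That argues against any intention to screen such patients out. It covers enrolled subjects only.
- **The all-cases aim.** Section 6.1 can be read as all eligible Trevo cases, so this is a tension rather than a flat contradiction.
- **Ordinary reading.** Many investigators may already take the criterion to mean comorbidity. The text does not say so.

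**Conclusion.** The point holds as a defect of wording that should be corrected. Criterion 5 does not set aside the index stroke, covers the same period as the Day 90 endpoints, and can let sites leave out severe treated strokes. The pre-procedure route follows from the literal text and does not depend on late consent. The post-procedure route is not provided for, but it is not closed either.

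The likely direction is lower mortality and a higher mRS 0-2 rate. The size is unknown. Under the assumed 2% to 5% left out, with 60% to 100% of them dead by Day 90, mortality shifts by about 0.6 to 4.2 points, against a half-width of about 1.8 to 2.1 points. At 2% the shift is within sampling error. A larger registry would not reduce it.

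Two stronger statements might be inferred and are not supported. The first is that entry depends on the outcome itself: it depends on anticipated survival, not observed survival. The second is that severe cases are in fact being removed: the protocol shows only that they could be.

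**What to change.** Reword criterion 5 in section 7.1.1, its synopsis copy and the matching eCRF item along these lines: 'No condition other than the index stroke and its treatment that is expected to limit life to less than 3 months, judged on information available before arterial puncture, including when consent is obtained later.'

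It would also help if the screening log counted Trevo-treated patients left out under this criterion, so that any remaining loss is visible.

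The cost is one criterion and one form item. No sample-size figure changes. The one small downside is that reported mortality may be somewhat higher, because it would then come closer to mortality in all treated cases.

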7.2 Withdrawal and Replacement of Subjects

While study withdrawal is discouraged, subjects may withdraw from the study at any time, with or without reason and without prejudice to further treatment. Withdrawn subjects will not undergo any additional follow-up, nor will they be replaced. If a subject chooses to withdraw from the registry, the reason(s) for withdrawal will be recorded on the appropriate eCRF and in the medical record.

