9.2 Analysis Populations

The Intent-to-treat principle will be followed to define the analysis population. All of the subjects who signed the informed consent and in whom Trevo Retriever was deployed through the microcatheter are considered enrolled and will be included in the analyses.

Sub-group analyses for the Registry will be performed under guidance from the Study PIs, Steering Committee, and Sponsor.

Day 90 outcomes will be compared to pre-stroke mRS status, baseline imaging and time of symptom onset to treatment. The first interim analysis will be performed after 300 subjects are enrolled and the results will be reported. Additional interim analyses and data reporting will occur throughout the study enrollment period.

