It is important that the Investigator and relevant study site personnel are available during monitoring visits and that sufficient time is devoted to the process. In order to perform her or his role well, the monitor must be given access to primary subject medical records which support the registry eCRFs. This access must be disclosed to the subject via the informed consent.

The investigator agrees to complete all registry requirements within three months of written notice of enrollment completion. Continuation of the registry beyond this time must be mutually agreed upon in writing by both the investigator and Stryker Neurovascular.

Stryker Neurovascular will conduct a registry closeout meeting with each Trevo Registry site after the final data query is generated and data requests are addressed. The purpose of the closeout meeting is to confirm that all registry-related activities are complete and site personnel are aware of the regulatory obligations following study closure activities. The closeout meeting may transpire remotely e.g. teleconference or at an on-site monitoring visit. The closeout activities include but are not limited to the following:

- Final regulatory document review and collection of any outstanding documents including a copy of the investigator notification letter sent to the IRB/EC regarding completion of the Trevo Retriever Registry
- Address and close any open action items
- Discuss record retention requirements
- Review publication guidelines

12 Auditing

Sites may be subject to a quality assurance audit by Stryker Neurovascular or its designees, or other regulatory authorities.

Trevo[®] Retriever Registry

It is important that the Investigator and relevant study personnel are available during any audits and that sufficient time is devoted to the process.

13 Device Accountability

There will be no device accountability or tracking as the Trevo Retriever has regulatory authorization to market the device.

14 Adverse Events

The following adverse events will be reported:

- all adverse events that occur during the procedure
- all SAEs related to the device or the procedure through Day 90
- all adverse events that result in death through Day 90

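### Section 7.2 ends all follow-up at withdrawal, with no exception for a records-based check of Day 90 vital status and related serious adverse events

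*Protocol*

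**What the plan says.** Section 7.2 provides that "subjects may withdraw from the study at any time, with or without reason", and then that "Withdrawn subjects will not undergo any additional follow-up, nor will they be replaced". The one item it tells the site to capture is why the subject left: "the reason(s) for withdrawal will be recorded on the appropriate eCRF and in the medical record". It does not distinguish a subject who wants no more visits or calls from one who wants no more data collected.

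Other parts of the protocol want outcomes on every enrolled subject:

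- Section 9.2: "The Intent-to-treat principle will be followed to define the analysis population". Consented subjects in whom the device was deployed "are considered enrolled and will be included in the analyses". Withdrawal is not a ground for exclusion.
- The synopsis lists "Day 90 all cause mortality" as a secondary endpoint, next to Day 90 mRS (Section 5.2 defines a good outcome as 0–2).
- Section 14 requires reporting of "all adverse events that result in death through Day 90", and of device- or procedure-related serious adverse events over the same period.
- Section 8.6.2 asks for whatever is known about the cause and time of death for every subject who dies before the Day 90 assessment.

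Neither Section 14 nor Section 8.6.2 carves out withdrawn subjects.

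**The concern.** Vital status at Day 90 can often be learned without a visit or a call. A site that follows Section 7.2 as written would not look for it, and would not look for late related serious events either, even where the subject would not have objected to a records check. The subject stays in the denominator under Section 9.2 with an outcome that was obtainable and was not sought.

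At stake are two of the four secondary endpoints, plus late related serious events, in a registry whose stated purposes (Section 6) include monitoring safety and detecting rare complications. Vital status also serves the mRS endpoint, because Appendix F scores death as 6. With a single arm, no comparator could absorb part of a bias. An analysis plan can describe or impute missing outcomes, but it cannot recover data that sites were told not to collect.

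**Working it through.** **Text.** Set side by side, Sections 7.2 and 9.2 are compatible: a subject can be in the analysis set with a missing outcome. Section 7.2 against Sections 14 and 8.6.2 is unreconciled. One stops all follow-up at withdrawal; the others ask for deaths through Day 90 with no exception.

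**Inputs.**
- N = 2000, the maximum in the synopsis.
- Day 90 mortality in Trevo-treated subjects: 12/60 = 20.0% (Table 1) and 29/88 = 33.0% (Table 4). 25% is an assumed value between them.
- Withdrawn fraction w: not given in the protocol. Assumed, and shown from 1% to 10%.

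**Bounds.** If a fraction w has unknown vital status and mortality among the rest is p:
- lower bound (all withdrawn subjects alive) = p(1 − w)
- upper bound (all withdrawn subjects dead) = p(1 − w) + w
- width = w, whatever p is.

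Example at p = 25%, w = 5%: 0.25 × 1900 = 475 deaths among those followed, and 100 unknown. The bounds are 475/2000 = 23.75% and 575/2000 = 28.75%.

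| w | Unknown | Bounds, p = 20% | Bounds, p = 25% | Bounds, p = 33% |
|---|---|---|---|---|
| 1% | 20 | 19.8–20.8% | 24.75–25.75% | 32.7–33.7% |
| 2% | 40 | 19.6–21.6% | 24.5–26.5% | 32.3–34.3% |
| 5% | 100 | 19.0–24.0% | 23.75–28.75% | 31.35–36.35% |
| 10% | 200 | 18.0–28.0% | 22.5–32.5% | 29.7–39.7% |

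**Sampling error for comparison.** The 95% half-width is 1.96 × √(p(1 − p)/2000). This gives 1.75 points at 20%, 1.90 at 25% and 2.06 at 33%, so full widths of about 3.5, 3.8 and 4.1 points. At 25% mortality the bounds become wider than the confidence interval only above about 3.8% withdrawal (0.038 × 2000 = 76 subjects).

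**Possible bias.** Full-cohort mortality minus complete-case mortality = w × (mortality in withdrawn − mortality in followed). With 25% in those followed:
- 40% in withdrawn: 0.05 × 15 = 0.75 points too low at 5% withdrawal; 0.10 × 15 = 1.5 points at 10%.
- 10% in withdrawn: 0.05 × (−15) = −0.75, so 0.75 points too high at 5%.

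The 40% and 10% are illustrations. The protocol supports neither sign over the other.

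**Can vital status be known without mRS?** Table 4 (TREVO 2) has mRS denominators of 85 of 88 and 87 of 90, so 3 + 3 = 6 of 178 missing (3.4%). The mortality denominators are 88 of 88 and 89 of 90, so 0 + 1 = 1 of 178 missing (0.6%). Vital status was therefore known for most subjects who lacked an mRS.

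**The case against.** Ending follow-up at withdrawal is a permissible choice for a low-burden registry. It can also be argued that a records search is not something a subject undergoes, so that Sections 7.2, 8.6.2 and 14 can be read together. Section 7.2 does not name vital status. The consent template in Appendix C is not in the text available here and may say what can be collected after withdrawal. The effect may be small: at 1–2% withdrawal the bounds sit well inside sampling error, the upper bound requires every withdrawn subject to have died, and no hypothesis test or threshold depends on the result. Most of this stands, and it limits the point to an unclear and needlessly broad rule. It does not remove the point: a site reading Section 7.2 would most naturally stop all collection, and nothing in the visible text tells it otherwise.

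Four stronger readings are tempting and are not supported:

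- A reader might infer that Sections 7.2 and 9.2 contradict each other. They do not; the result is missing data.
- A reader might infer that declining the Day 90 visit counts as withdrawal. Section 8.6.2 and Appendix D allow a telephone mRS when the subject cannot return, and nothing turns a missed visit into a withdrawal.
- A reader might take 3.4% from TREVO 2 as a withdrawal rate, or infer that Section 7.2 forbids what kept its mortality data nearly complete. The protocol describes neither that trial's withdrawal rule nor how it traced deaths.
- A reader might infer that mortality will be understated. A subject who withdraws in person is alive at that moment, and recovered subjects may leave too, so the bias could go either way.

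**Conclusion.** The point holds as an avoidable loss of secondary-endpoint and safety data. It is not an error that threatens the main result: the primary endpoint, modified TICI at the end of the procedure, is unaffected. Only withdrawals before Day 90 matter, and Section 7.2 does not discard events recorded before withdrawal.

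The size rests on a withdrawal rate that the protocol does not give. The uncertainty in Day 90 mortality equals that rate: minor at 1–2%, similar to sampling error near 4%, and larger from 5%. The conclusion also rests on the plain reading of Section 7.2 and on the consent template not already providing otherwise. It is worth correcting because the remedy is cheap and data not collected at Day 90, mRS above all, are hard to recover later.

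**What to change.** Amend Section 7.2 to define two levels of withdrawal: (a) from study visits and calls, and (b) of permission for any further data collection. Ask at the time of withdrawal which applies, and record the level and date on the eCRF.

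- Under (a), where consent and local rules permit, the site obtains Day 90 vital status (with date and cause of death) and device- or procedure-related serious adverse events from medical records or public sources, without contacting the subject. A telephone Day 90 mRS is taken only if the subject or representative agrees to that call when withdrawing.
- Under (b), collection stops.
- Data collected before withdrawal are retained as the consent form and local law allow.
- The no-replacement rule stays.

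Align Sections 8.6.2 and 14 with this wording, and the consent form if it does not already say so. The cost is a short amendment, one addition to the withdrawal eCRF, some site time for record checks, and possibly IRB/EC agreement for subjects already consented. No treatment or endpoint definition changes.
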